12.2 Analysis Sets

Six analysis sets will be used: the Overall Safety Analysis Set for any dose (SafAS), Safety Analysis Set for vaccination 1 (SafAS1), Safety Analysis Set for vaccination 2 (SafAS2), Safety Analysis Set for vaccination 3 (SafAS3), Safety Analysis Set for vaccination 4 (SafAS4), and Safety Analysis Set 5 for all 4-dose vaccinations (SafAS5).

12.2.1 Full Analysis Set

Not applicable to this study.

12.2.2 Safety Analysis Set

The SafAS is defined as those subjects who have received at least 1 dose of the study vaccine(s) ^a and have any safety data available. Specific safety analysis will be defined and used after each vaccination. Safety analysis after all 4-dose vaccinations will also be conducted as well.

All subjects will have their safety analyzed after each dose according to the vaccine they actually received, after any dose, and after all 4 doses according to the vaccine received at the first dose.

Safety data recorded for a vaccine received out of the protocol design will be excluded from the analysis (and listed separately).

12.2.2.1 Overall Safety Analysis Set for Any Dose

The overall SafAS is defined as those subjects who have received at least one dose of the study vaccines and have any safety data available. All subjects will have their safety analyzed after any dose according to the vaccine received at the first dose.

Safety data recorded for a vaccine received out of the protocol design will be excluded from the analysis (and listed separately).

12.2.2.2 Safety Analysis Set for Vaccination at 2 Months of Age

The SafAS1 is defined as those subjects who have received the study vaccine at Visit 1 around 2 months of age and have any safety data available. All subjects will have their safety analyzed after the Visit 1 dose according to the vaccine they actually received at Visit 1.

Safety data recorded for a vaccine received out of the protocol design at Visit 1 will be excluded from the analysis (and listed separately).

12.2.2.3 Safety Analysis Set for Vaccination at 4 Months of Age

The SafAS2 is defined as those subjects who have received the study vaccine at Visit 2 around 4 months of age and have any safety data available. All subjects will have their safety analyzed after this dose according to the vaccine they actually received at that visit.

Safety data recorded for a vaccine received out of the protocol design at Visit 2 will be excluded from the analysis (and listed separately).

12.2.2.4 Safety Analysis Set for Vaccination at 6 Months of Age

The SafAS3 is defined as those subjects who have received the study vaccine at Visit 3 at around 6 months of age and have any safety data available. All subjects will have their safety analyzed after this dose according to the vaccine they actually received at this visit.

^a A study vaccine is any vaccine that is administered as part of the study, including the investigational product (MenACYW conjugate vaccine), the control vaccine (Menveo), and the routine vaccines .

Safety data recorded for a vaccine received out of the protocol design at Visit 3 will be excluded from the analysis (and listed separately).

12.2.2.5 Safety Analysis Set for Vaccination at 12 Months of Age

The SafAS4 is defined as those subjects who have received the study vaccine at Visit 4 at around 12 months of age and have any safety data available. All subjects will have their safety analyzed after this dose according to the vaccine they actually received at that visit.

Safety data recorded for a vaccine received out of the protocol design at Visit 4 will be excluded from the analysis (and listed separately).

12.2.2.6 Safety Analysis Set for all 4-dose Vaccinations

The SafAS5 is defined as those subjects who have received all 4 doses of the study vaccine (3 doses in infancy and 1 dose in the second year of life at 12 months of age) and have any safety data available. All 4-dose vaccinations received in a series should be either all MenACYW conjugate vaccine or all MENVEO[®].

Safety data recorded for subjects not receiving all 4 doses of MenACYW or MENVEO[®] will be excluded from the analysis (and listed separately).

12.2.3 Per-Protocol Analysis Set

Not applicable to this study.

12.2.4 Populations Used in Analyses

The safety analysis will be performed on the Safety Analysis Sets SafAS, and SafAS1 through SafAS5.

12.3 Handling of Missing Data and Outliers

12.3.1 Safety

No replacement will be done.

12.3.2 Immunogenicity

No immunogenicity data will be collected.

12.3.3 Efficacy

No efficacy data will be collected.

12.4 Interim / Preliminary Analysis

No interim / preliminary analyses are planned.

12.5 Determination of Sample Size and Power Calculation

The sample size of this study was chosen to provide safety data; it is not intended for the purposes of hypothesis testing. No formal sample size calculation is performed.

Though there are no statistically powered hypotheses, the overall study cohort of 3080 subjects will provide a probability of approximately 95% of observing any AE with a true incidence of 0.15%. In the treatment arm with 2310 subjects, there is a probability of approximately 95% of observing any AE with a true incidence of 0.2%.

13 Ethical and Legal Issues and Investigator / Sponsor Responsibilities

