	• Occurrence, nature (MedDRA preferred term), time of onset, duration, intensity, action taken, relationship to vaccination, and whether the event led to early termination from the study for MAAEs throughout the trial, from Visit 1 to the 6-month follow-up contact after the last vaccination.
Planned Sample Size:	Approximately 3080 subjects are planned to be enrolled:
	Group 1 (MenACYW conjugate vaccine): n = 2310
	Group 2 (MENVEO®): n = 770
Schedule of Study Procedures:	Vaccination
	All subjects will receive a dose of entirel MenAC 1 w conjugate vacchie of MENVEO [®] with routine pediatric vaccines at 2, 4, 6, and 12 months of age. All subjects will receive the routine pediatric vaccines as per the approved ACIP recommended schedules: Pentacel [®] at 2, 4, and 6 months of age*; PREVNAR 13 [®] at 2, 4, 6, and 12 months of age; RotaTeq [®] at 2, 4, and 6 months of age; ENGERIX-B [®] at 2 and 6 months of age [†] ; and M-M-R [®] II and VARIVAX [®] at 12 months of age.
	Study vaccines will be administered according to the following schedules:
	Group 1 : MenACYW conjugate vaccine and routine pediatric vaccines will be administered at 2, 4, 6, and 12 months of age.
	Group 2 : MENVEO [®] vaccine and routine pediatric vaccines will be administered at 2, 4, 6, and 12 months of age.
	* All subjects will complete the last study visit at 13 to 14 months of age. For all subjects, the 4 th dose of Pentacel [®] should be administered by site personnel at 15 to 18 months of age as per standard practice. The 4 th dose of Pentacel [®] will be provided by the Sponsor for completion of the DTaP series with vaccine from the same manufacturer, to ensure compliance with the ACIP recommendation.
	[†] First dose of hepatitis B vaccine must be given at least 28 days prior to study enrollment.
	Blood sampling
	No blood samples will be collected as this is a safety study.
	Collection of safety data
	• All subjects will be followed for safety from Visit 1 to 6 months after the last vaccinations at 12 months of age.

	• All subjects will be observed for 30 minutes after each vaccination, and any unsolicited systemic AEs occurring during that time will be recorded as immediate unsolicited systemic AEs in the CRB.
	• The subject's parent / guardian will record information in a diary card about solicited reactions from D0 to D07 after each vaccination and unsolicited AEs from D0 after each vaccination to the next study visit.

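### On the plain reading, 3080 and 2310 subjects give a 99.0% chance, not about 95%, of observing an AE at 0.15% and 0.2%; the correction is to wording only

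*Protocol*

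**What the plan says.** Protocol 12.5 explains that the size was chosen to provide safety data and that "No formal sample size calculation is performed". It then makes two quantitative claims. The first is that "the overall study cohort of 3080 subjects will provide a probability of approximately 95% of observing any AE with a true incidence of 0.15"%. The second reads: "In the treatment arm with 2310 subjects, there is a probability of approximately 95% of observing any AE with a true incidence of 0.2"%. The same two sentences stand in the Synopsis (Sample Size Calculation) and in SAP 5.5.

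The numbers attached to the 95% are the enrolment targets. The Synopsis (Planned Sample Size) says "Approximately 3080 subjects are planned to be enrolled", with 2310 in the MenACYW group and 770 in the MENVEO group. None of the three places says how many events count as observing an AE, and none gives a dropout rate or an evaluable number. Protocol 5.2.8 says that withdrawn subjects are not replaced.

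**The concern.** Each sentence supplies a number of subjects, an incidence and a probability, so each can be checked in one line, and neither passes. Because there is no formal sample size calculation and no hypothesis (Protocol 12.1.1.1, SAP 5.1.1.1), these sentences are the only quantitative description of what the chosen size can observe, in a trial that Protocol 5.1.2 presents as a pivotal safety study.

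The stake is how the safety database is read. Someone citing these sentences would either understate the trial's sensitivity to rare events by a factor of about 1.5 or, if a stricter criterion was intended, not know that it applies. Enrolment, the analysis sets, the estimates and subject safety do not depend on the figure.

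**Working it through.** **Inputs** (Protocol 12.5, repeated in the Synopsis and SAP 5.5): n = 3080 with p = 0.0015; n = 2310 with p = 0.002; stated probability about 0.95 for each. The event count is not stated, so at least one is taken as the plain reading.

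**Step 1. Attempt to reproduce the stated figure.** P(at least one) = 1 − (1 − p)^n.

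- Overall: 1 − 0.9985^3080 = 0.9902
- MenACYW arm: 1 − 0.998^2310 = 0.9902

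Expected events are 3080 × 0.0015 = 4.62 and 2310 × 0.002 = 4.62. The Poisson form, 1 − e^(−4.62), gives 0.9901. The 95% is not reproduced: the chance of seeing no case is about 1%, not about 5%.

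**Step 2. Incidence that matches 95%.** p = 1 − 0.05^(1/n).

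- n = 3080: 0.000972, or 0.097%; 0.0015 / 0.000972 = 1.54
- n = 2310: 0.001296, or 0.130%; 0.002 / 0.001296 = 1.54

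The incidences that give exactly 99% are 1 − 0.01^(1/n) = 0.149% and 0.199%, which round to the printed 0.15% and 0.2%. Both sentences are off by the same factor, so this is not a slip in a single number.

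**Step 3. Conditions that would return about 95%.**

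- *At least two events at full n.* 1 − (1 − p)^n − np(1 − p)^(n−1) = 1 − 0.0098 − 0.0454 = 0.9448 for both pairs. At least three gives 0.840.
- *At least one event at a smaller n.* n = ln 0.05 / ln(1 − p) = 1995.7 at 0.15% and 1496.4 at 0.2%. Each is 64.8% of the planned number, so about 35% loss. Multiplying the planned numbers by 0.65 gives 2002 (3080), 1501.5 (2310) and 500.5 (770). At 2000 and 1500, 1 − 0.9985^2000 and 1 − 0.998^1500 both equal 95.0%.

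**Step 4. Effect of loss.** The documents give no rate, so the rates below are assumptions. Results agree for the two sentences to about 0.1 point.

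| Assumed loss | At least one | At least two |
|---|---|---|
| 0% | 99.0% | 94.5% |
| 10% | 98.4% | about 92% |
| 20% | 97.5% | 88.4% |
| 30% | 96.1% | 83.3% |
| 35% | about 95% | about 80% |
| 40% | 93.8% | 76.4% |

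**Step 5. Check of replacement incidences.** 1 − 0.999^3080 = 0.954 and 1 − 0.9987^2310 = 0.950.

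**The case against.** The arithmetic is not in dispute. The strongest reply is that an error is not proven: at least two events reproduces both figures at the stated numbers, so what is established is an undefined event count. It follows that conservative is a conditional description. Under at least two events, 94.5% is a fair rounding at full n, and any loss makes it optimistic. This stands, and the direction is claimed here only for at least one event. It does not rescue the text. Observing an AE ordinarily means seeing at least one, and a two-event criterion appears in none of the three places.

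A second reply is that 35% loss has no support. In MET39, 580 were enrolled (Protocol 1.2.1.1) and 457 completed (Protocol 5.1.2), a loss of 123/580 = 21%. Borrowed as an assumption, that rate leaves about 2427 and 1820 subjects: 97.4% for at least one event and 87.8% for at least two. The overall safety set also needs only one dose and some safety data (Protocol 12.2.2.1), so later dropout would hardly shrink it. These points weaken the attrition explanation without excluding it. Taking 65% of the planned numbers lands close to 2000, 1500 and 500, and the first two give 95.0% at the printed incidences. The 95% may therefore belong to an evaluable number that the text does not mention.

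Third, no analysis uses the figure, and a correction probably comes too late to inform the choice of size. Inclusion was planned to end in September 2019 (Protocol 5.1.5), while the SAP already covers COVID-19 (5.1.1.2.2.3). That limits the consequence but does not make the figure right.

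**Conclusion.** The concern holds. With at least one event, which is the plain reading, the stated numbers and incidences give 99.0% in both sentences, about 4 points above the claim; alternatively, the incidences are 1.54 times those that match 95%. On that reading the error is conservative at full n, and the probability stays at or above 95% until about 35% of subjects are lost. Every route back to about 95% needs a condition that the documents do not state, so either the figure is wrong or its defining condition is missing.

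The 99.0% rests on the full planned numbers, independent subjects and a common incidence. Which condition the sponsor had in mind cannot be settled from the documents. This should be corrected, but it is a matter of wording and does not call the trial's size or analyses into question.

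**What to change.** Ask the sponsor which condition was meant, then make the same change in the Synopsis, Protocol 12.5 and SAP 5.5:

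- **At least one event, all enrolled subjects:** say so, and either keep 0.15% and 0.2% and write 99%, or keep 95% and write 0.10% for 3080 (gives 95.4%) and 0.13% for 2310 (gives 95.0%).
- **At least two events:** the numbers, incidences and approximate 95% can stay (exact value 94.5%), and the two-event criterion must be added.
- **At least one event in an evaluable number:** state the assumed attrition and that number (about 2000 and 1500), and attach the 95% to it rather than to 3080 and 2310.

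The cost is one pair of sentences in three places, with no change to enrolment or analyses. Under Protocol 5.4, a protocol change that affects neither scientific quality nor subject safety is an administrative amendment, which is notified to the ethics committees without formal approval.

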13.1 Ethical Conduct of the Study / Good Clinical Practice

The conduct of this study will be consistent with the standards established by the Declaration of Helsinki and compliant with the ICH guidelines for GCP as well as with all local and / or national regulations and directives.

13.2 Source Data and Source Documents

"Source data" are the data contained in source documents. Source documents are original documents or certified copies, and include, but are not limited to, diary cards, medical and hospital records, screening logs, informed consent / assent forms, telephone contact logs, and worksheets. The purpose of study source documents is to document the existence of subjects and to substantiate the integrity of the study data collected. Investigators must maintain source documents so that they are accurate, complete, legible, and up to date.

For missing or discrepant data on a diary card, the study coordinator will obtain verbal clarification from the subject, enter the response into the "Investigator's comment" page of the diary card, and transfer the information to the CRB.

The subject pre-screening log should list all individuals contacted by the Investigators to participate in the study, regardless of the outcome.

The Investigator must print^a any electronic records on an ongoing basis, sign and date them immediately after creation, and keep the printouts on file as source documents that can be verified by the Sponsor or an inspector against the electronic records. Any subsequent changes of an

^a Unless the electronic medical records are managed by validated computerized systems that are compliant with US 21 CFR Part 11, in which case they are acceptable on their own.

electronic record require the record to be re-printed, dated (with an indication of the date of change), and signed. Such records must also be kept together with the original printed copy.

Good Documentation Practice should be followed by the Investigator and the site staff managing source documents.

13.3 Confidentiality of Data, Data Protection and Access to Subject Records

Prior to initiation of the study, the Investigator will sign a fully executed confidentiality agreement with Sanofi Pasteur. In the event a subject's medical records are not at the investigational site, it is the responsibility of the Investigator, to obtain those records if needed.

All personal data collected related to subjects, Investigators, or any person involved in the study, which may be included in the Sponsor's databases, shall be treated in compliance with all applicable laws and regulations, including the Global Data Protection Regulation (GDPR). Data collected must be adequate, relevant and not excessive, in relation to the purposes for which they are collected. Each category of data must be properly justified and in line with the study objective.

Subjects' race and ethnicity will be collected in this study because these data are required by the FDA in the US (57).

Subjects will be assigned a unique identifier by the Sponsor. Any subject records or datasets that are transferred to the Sponsor will contain the identifier only; subject names or any information that would make the subject identifiable will not be transferred.

The subject must be informed that his/her personal study-related data will be used by the Sponsor in accordance with local data protection law. The level of disclosure must also be explained to the subject.

The subject must be informed that his/her medical records may be examined by Clinical Quality Assurance auditors or other authorized personnel appointed by the Sponsor, by appropriate IRB/IEC members, and by inspectors from regulatory authorities.

When archiving or processing personal data pertaining to the Investigator and/or to the subjects, the Sponsor shall take all appropriate measures to safeguard and prevent access to this data by any unauthorized third party.

13.4 Monitoring, Auditing, and Archiving

13.4.1 Monitoring

Before the start of the study (i.e., before the inclusion of the first subject) in the first center the Investigators and the Sponsor's staff or a representative will meet at the site-initiation visit to discuss the study protocol and the detailed study procedures. Emphasis will be placed on inclusion and exclusion criteria, visit timing, safety procedures, informed consent procedures, SAE reporting procedures, CRB completion, and the handling of products. The Sponsor's staff or a representative will ensure and document that all material to be used during the study has been received at the site; and that the study investigator team and local Sponsor/delegate staff have been properly informed about the study, GCP and regulatory requirements, and the Sponsor's

procedures. Specific training sessions for the study investigator team and the CRAs on these topics may be performed as necessary, and should be documented.

The following instruction manuals will be provided: the CRF Completion Instructions for entering data into the CRB, and the Operating Guidelines for detailed study procedures such as the product management.

After the start of the study, the Sponsor's staff or a representative will be in regular contact with the investigational team through telephone calls and regular follow-up visits. The Investigator or delegate must be available for these visits, and must allow the Sponsor/delegate staff direct access to subject medical files and CRBs. During these visits, the Sponsor/delegate staff will:

- Evaluate the quality of the study progress (adherence to protocol and any study-specific guidelines, quality of data collection and document completion, signature of consent forms, occurrence of SAEs, product management, cold-chain monitoring, archiving)
- Source-verify completed CRBs and any corresponding answered queries
- Determine the number of complete or ongoing issues identified at monitoring visits (e.g., protocol deviations, SAEs). Any identified problems will be discussed with the Investigator, and corrective or preventive actions will be determined, as appropriate.

After all protocol procedures have been completed and the data have been entered into the CRB, the Investigator must still be available to answer any queries forwarded by the Sponsor. All data-related queries must be completed prior to database lock.

At the end of the study, a close-out visit will be performed to ensure that:

- The center has all the documents necessary for archiving
- All unused materials and products have been either destroyed or returned to the Sponsor

13.4.2 Audits and Inspections

A quality assurance audit may be performed at any time by the Sponsor's Clinical Quality Assessment department (CQA) or by independent auditors to verify that the study has been conducted according to the protocol, GCP and ICH requirements, and other applicable regulations. An inspection may be conducted by regulatory authorities. The Investigator must allow direct access to study documents during these inspections and audits.

13.4.3 Archiving

The Investigator must keep all study documents after the completion or discontinuation of the study, whatever the nature of the investigational center (private practice, hospital, or institution), for as long as required by applicable laws and regulations. In the absence of any applicable laws or regulations, study documents will be kept at a minimum for the duration indicated on the Clinical Trial Agreement (CTA). In no event, should study personnel destroy or permit the destruction of any study documents upon less than 90 days advance written notification to the Sponsor. In addition, study documents should continue to be stored, at Sponsor's sole expense, in the event that the Sponsor requests in writing that such storage continues for a period of time that exceeds that required by any applicable law or regulation or the CTA. The Investigator will

inform Sanofi Pasteur of any address change or if they will no longer be able to house the study documents.

Archived data may be held on electronic records, provided that a back-up exists and that a hard copy can be obtained if required. The protocol, documentation, approvals, and all other documents related to the study will be kept by the Sponsor in the Trial Master File (TMF). Data on AEs are included in the TMF. All data and documents will be made available if requested by relevant authorities.

13.5 Financial Contract and Insurance Coverage

A CTA will be signed by all the parties involved in the study's performance, if relevant. The Sponsor has an insurance policy to cover any liabilities that may arise from use of the product and / or the study protocol.

13.6 Stipends for Participation

The subject's parent / guardian may be provided with a stipend according to local practice to compensate for the time and travel required for study visits and procedures.

UAR unexpected adverse reaction

V visit

1 Introduction

This study (MET41) will evaluate the safety of a 4-dose series of the quadrivalent Meningococcal Polysaccharide (Serogroups A, C, Y, and W) Tetanus Toxoid Conjugate Vaccine (hereafter referred to as MenACYW conjugate vaccine) in children starting immunization at 6 weeks of age. The purpose of the MET41 study is to demonstrate that the safety profile of the MenACYW conjugate vaccine is similar to that of MENVEO® when administered concomitantly with routine pediatric vaccines given to healthy infants and toddlers in the United States (US) and Puerto Rico.

Invasive meningococcal disease (IMD) is a serious illness caused by the bacterium *N. meningitidis*, a Gram-negative diplococcus found exclusively in humans. Symptoms may include intense headache, fever, nausea, vomiting, photophobia, stiff neck, lethargy, myalgia, and a characteristic petechial rash (1). Worldwide, most cases of meningococcal disease are caused by serogroups A, B, C, X, Y, and W (2) (3) (4).

The epidemiology of *N. meningitidis* can be described as complex, unpredictable, geographically variable, and changing over time. Meningococcal disease occurs worldwide in both endemic and epidemic forms with seasonal variation. In Europe, the incidence rate of IMD has remained stable over the last 5 to 10 years, with the highest peak occurring in the population less than 4 years of age and a smaller peak in the 15 to 19 years old group. The highest incidence rate in Europe is caused by serogroup B, followed by C (5). In the US, the incidence rate of IMD was 0.14 per 100,000 in all ages; 0.83 per 100,000 in infants less than 1 year; 0.62 per 100,000 in toddlers 1 year of age; 0.27 per 100,000 in children 2 to 4 years of age; and 0.02 per 100,000 in children 5 to 17 years of age in 2013. The age specific incidence rate per 100,000 was 0.08 in adults 50 to 64 years of age, 0.03 in adults 65 to 74 years of age, 0.14 in adults 75 to 84 years of age, and 0.43 in adults 85 years of age and older in 2013 (6).

The goal for MenACYW conjugate vaccine is to provide broad protection against IMD caused by serogroups A, C, Y, and W in all age groups including children as young as 6 weeks of age, adolescents, and adults, including those 56 years of age and older.

The MenACYW conjugate vaccine formulation was finalized based on data provided by 2 studies: MET28, a Phase I study in infants, toddlers, and adults 18 to < 40 years of age; and MET32, a Phase I/II study in toddlers. The formulation has been evaluated in around 7115 subjects (infants, toddlers, adolescents, and adults > 56 years of age) in 10 completed studies: 4 Phase II studies in the US (MET39, MET44, MET50) and Finland (MET54); and 6 Phase III studies in the US (MET35, MET43, MET49, MET56), EU region (Spain, Germany, Hungary and Finland [MET51]), and in Thailand, South Korea, Russia, and Mexico (MET57). MenACYW conjugate vaccine was found to be well tolerated and no unanticipated or new significant safety concerns have been identified in the clinical trials completed to date.

The purpose of the MET41 study is to describe the safety profile of the MenACYW conjugate vaccine and the comparator MENVEO® when administered concomitantly with routine pediatric vaccines given to healthy infants and toddlers in the US. MET41 study will generate data which will significantly contribute towards the overall safety database of the MenACYW conjugate vaccine in the US and in general.

2 Study Objective

To describe the safety profile of MenACYW conjugate vaccine and MENVEO[®] when administered concomitantly with routine pediatric vaccines in healthy infants and toddlers. The endpoints for the study objective are presented in Section 4.1.1.2.

3 Description of the Overall Study Design and Plan

